NCT06267222

**Trans-spinal Electrical Stimulation in
Individuals with Spinocerebellar Ataxia**

October, 2023

Abstract

The main goal of this pragmatic clinical trial is to investigate the effects of trans-spinal tDCS in individuals with spinocerebellar ataxia (SCA) over some parameters of gait and postural control in real-world conditions, reflecting daily clinical practice. The main questions it aims to answer are: (i) If an extended number of tDCS sessions, beyond the typical 5 to 10 sessions described in scientific literature, applied concomitantly with exercises with progressive challenges, to yield positive outcomes over some parameters of gait and postural control in individuals with SCA and if there is retention of possible benefits one month later the end of this protocol; (ii) If there is specific characteristics (including balance, gait, mobility, severity of ataxia, DNA test characteristics and non-ataxic signs) in individuals with SCA that can predict their improvement in postural control and gait following the 20 tDCS sessions. Participants will receive 20 tDCS sessions concomitantly with exercises for gait and postural control with progressive challenges. Postural control and gait of the participants will be assessed in two big sessions before (#assessment 1) and after the 20 sessions (#assessment 5) and 3 small sessions after every 5 sessions (#assessments 2, 3 and 4). Also, as a follow-up, they will be assessed a month after the end of the intervention (#assessment 6).

1. Scientific background

Spinocerebellar ataxias (SCA) comprise a group of progressive degenerative diseases, currently lacking pharmacological treatments. These conditions produce gait and balance disorders, ultimately necessitating the use of assistive devices, culminating in wheelchair dependency upon the loss of ambulatory function during the clinical progression of SCA. This significantly impacts the individual's independence and quality of life. Recent clinical trials have demonstrated that the application of transcranial direct current stimulation (tDCS) over the cerebellum and spinal cord (trans-spinal stimulation) has led to improvements in upper limb coordination, gait ataxia severity, motor scores (including balance), cognitive abilities, and quality of life in individuals with degenerative ataxias, including SCA. However, it is not yet known whether all patients with SCA demonstrate significant improvement with this intervention. Moreover, if there is no improvement, it remains unclear whether specific characteristics of individuals with SCA, such as balance, gait, mobility, ataxia severity, DNA test results, and non-ataxic signs, can be identified to predict their response to tDCS sessions. Additionally, tDCS studies in individuals with SCA typically involve 5 to 10 stimulation sessions without associating stimulation with exercises of progressive difficulty. One of the main benefits of using tDCS is the

plastic modulation of the nervous system. Therefore, the lack of challenges concomitant with the use of tDCS limits its results.

2. Aim

The main goal of this pragmatic clinical trial is to investigate the effects of trans-spinal tDCS in individuals with SCA over some parameters of gait and postural control in real-world conditions, reflecting daily clinical practice. The specific aims of this study are: (i) Determine whether particular characteristics of individuals with SCA (including balance, gait, mobility, severity of ataxia, DNA test characteristics and non-ataxic signs) can be identified to predict their improvement in balance and gait following tDCS sessions; (ii) to investigate if an extended number of tDCS sessions, beyond the typical 5 to 10 sessions described in scientific literature, applied concomitantly with exercises with progressive challenges, to yield positive outcomes over some parameters of gait and postural control in individuals with SCA; (iii) To investigate, through semi-structured interviews, the subjective experience of the participants regarding the use of trans-spinal tDCS, about changes in health and quality of life, as well as the expectations that were achieved or frustrated with the intervention used; (iv) To investigate if there is retention of benefits a month after the end of the intervention; (v) propose a specific test to detect postural control deficits during head and limb movement; and (vi) analyze whether the specific characteristics evaluated in individuals correlate with each other.

3. Design and Methods

This is a pragmatic clinical trial that will be carried out using the CONSORT-Pragmatic Trials. The present study will be carried out at the Deolindo Couto Institute of Neurology, at the Federal University of Rio de Janeiro - UFRJ ([name]). Individuals with spinocerebellar ataxia of any type, who are part of the records of public hospitals, doctors' offices, and physiotherapists, will be invited to participate in the study.

Initially, individuals will be interviewed to research the eligibility criteria, by filling out an anamnesis form, which will also contain questions about their

demographic data. Those who are eligible and agree to participate must express their consent by signing an informed consent form.

Up to 45 patients with SCA of different types will undergo a non-invasive stimulation plus gait and postural control training. The total duration of sessions will last 30 minutes during which participants will simultaneously receive 20 min of trans-spinal tDCS and perform a gait training protocol with progressively greater difficulties, previously tested in patients with SCA. The trans-spinal tDCS will be applied at an intensity of 2mA, with the anodic electrode positioned over the cerebellar region and the cathodic electrode over the thoracic region of the spinal cord (approximately vertebra T11). The intervention will be applied over four consecutive weeks on weekdays except weekends, totaling 20 sessions.

All participants will receive real stimulation, so there will be no control group. Given that it may be difficult to recruit additional SCA individuals willing to participate in a control group or to find patients with similar characteristics who do not receive treatment during the study period, also due to the progressively debilitating condition of the participants (SCA) and given their socio-economic conditions that limit their transportation, it would be ethically questionable to deprive a group of patients of receiving a potentially beneficial treatment, especially when there is no established standard therapy or other effective treatment options available to them.

The equipment to be used for stimulation will be an NKL Stimulator. The continuous current offered will be supplied through a pair of 5x7 cm (35 cm²) electrodes wrapped in sponges moistened with saline solution. The anode electrode will be positioned over the cerebellar region. To do this, the inion region will be located. Using a measuring tape, the point 2cm above the inion will be identified and the electrode will be fixed to the scalp, using appropriate adjustable bands. The cathode electrode will be positioned over the spinal region, more precisely, at the level of T8. To precisely find this position, the thoracic spinous processes will be palpated, and the 11th process located. Using a measuring tape, identify the point located 2 cm below T11 and fix the electrode with adhesive tape at this point. The stimulation intensity will be 2mA.

Initially, participants will be evaluated (ASSESSMENT 1) through the application of the SARA scale; modified dynamic gait index (mDGI); The Berg Balance Scale; Timed up and go (TUG); Inventory of non-ataxic signs (INAS);

The four-stage test; Ten-meter walk test with an accelerometer; and perform other three tasks using an accelerometer of a mobile phone: (i) 5 times sit-to-stand; (ii) Functional Reach Test; and (iii) a test consisted in move arms and head standing with foot together. Three physiotherapist experts in these evaluations who will not participate in the intervention sessions will conduct this part. Then, 20 successive tDCS sessions will be applied to the participants. Every 5 tDCS sessions, the mDGI and TUG assessment will be reassessed (ASSESSMENT 2, 3, and 4). At the end of the 20 sessions, all instruments will be reapplied except for INAS (ASSESSMENT 5). A month after the end of the intervention the individuals will be reassessed except for the tests using the accelerometer (ASSESSMENT 6).

Before and after each session, individuals will be evaluated using the one-leg stand test proposed in the miniBestest instrument. In this test, the individual must remain standing, with their eyes open and fixed on a point 1.6 to 3m away with their hands on their waist. The participant must remove a lower limb from the support, without assistance, flexing it backward and remaining there. The time spent in the position will be measured in seconds, from the moment the evaluator says "now" until the elevated foot touches the ground again, or the upper limbs move from the initial position. The test will be repeated twice for each lower limb. Both times will be noted, and the highest time will be considered.

At the end of 20 sessions, individuals who complete the intervention will be also interviewed with a semi-structurally questionnaire by a researcher who did not take part in the study. The method that will be used to analyze the interviews will be the framework approach, which consists of a deductive form of analysis that starts from pre-defined research objectives. The framework approach is a systematic method that allows for in-depth analysis, in which the researcher extracts codes from the interviewees' statements, forms categories, and finally acquires refined themes useful for describing the participants' ideas and perceptions. All interviews will be conducted face-to-face. The interviews will be recorded for future transcription, using a smartphone. Once the interviews have been transcribed, the content will be analyzed using ATLAS.ti® software, and, finally, the themes that most faithfully represent the concepts found in the interviews will be chosen.

Inclusion Criteria:

1. Individuals aged 18 to 70, without distinction of gender or ethnicity;
2. Diagnosed with spinocerebellar ataxia, of any type, by a neurologist;
3. With mild to moderate ataxia severity;
4. Able to walk 2 meters even when using a walker, cane or crutch;
5. Score ≥ 21 (BERTOLUCCI et al., 1994) on the Mini-Mental State Examination (MMSE; FOLSTEINet al., 1975; ALMEIDA, 1998);
6. No other concomitant neurological changes.

Exclusion Criteria:

1. Illiterate;
2. Being subjected to any other experimental physiotherapeutic or medicinal intervention during the clinical trial;
3. Skin condition that may affect the electrode placement site
4. Musculoskeletal, neurological or cardiorespiratory disorders that prevent the tests from being carried out;
5. Epilepsy;
6. Pregnancy;
7. History of brain surgery;
8. History of seizures;
9. Metallic implants in the skull that interfere with neuromodulation;

Outcome Measures**Primary Outcome Measure:****1. Postural control**

The Berg Balance Scale (BBS) measures functional balance and fall risk in 14 tasks. Each item is given a score of 0-4, with a total score between 0 and 56, being the higher the score, the better the individual's performance. The Berg scale also predicts the risk of falls. A score equal to or less than 45 points indicates a greater risk of falls.

The four-stage test (4-stage) assesses static balance and measures an individual's ability to hold a series of four balance positions, each more challenging than the previous, for at least 10 seconds each.

[Time Frame: (i) Baseline, (ii) after 20 sessions and (iii) in follow up (one month).]

2.Mobility

Timed up and go (TUG) assesses mobility, balance, walking ability and the risk of falling. On the command "go", the patient gets up from the chair, walks 3 meters, turns around, returns to the chair, and sits down. The time is calculated in seconds. The longer the time taken, the greater the risk of falling

[Time Frame: (ii) Baseline, (ii) at the end of sessions 5, 10, 15 and 20 (each session is 1 day) and (iii) in follow up (one month)]

3.Gait performance

Measured by the Modified Dynamic Gait Index (mDGI) which total score is from 0 (severe gait impairment) to 64 (no gait impairment) and a Ten-meter walk test with an accelerometer fixed at the sacrum to assess step and stride time, speed, and gait cadence.

[Time Frame: (ii) Baseline, (ii) at the end of sessions 5, 10, 15 and 20 (each session is 1 day) and (iii) in follow up (one month)]

4.Accelerometry

To perform three tasks using an accelerometer of a mobile phone fixed on the participant's waist: (i) 5 times sit-to-stand; (ii) Functional Reach Test; and (iii) a test consisted in move arms and head standing with foot together. The accelerometer will register how the body is moving and changing speed over time while performing tasks.

[Time Frame: (i) Baseline and (ii) after 20 sessions.]

Secondary Outcome Measures:

The subjective experience of the participants regarding the protocol.

Semi-structured interview regarding subjective experience of the participants relative to the study intervention

[Time Frame: At the end of session 20 (each session is 1 day)]

The presence of non ataxic signals (INAS) and the disease severity (SARA)

INAS is an inventory to detect the presence or absence of 16 non-ataxic signs and symptoms through a clinical physical examination. SARA is an instrument to

evaluate the disease severity through eight tasks including gait, balance, speech and coordination that produce a total score of 0 (no signs of ataxia) and 40 (more severe ataxia).

[Time Frame: (i) Baseline and (ii) after 20 sessions.]

References

ALMEIDA, OP Mini mental state examination and the diagnosis of dementia in Brazil. Archives of Neuro-Psychiatry, v. 56, n. 3B, p. 605–612, Sept. 1998.

BARRETO, TL. et al. Transcranial direct current stimulation in the treatment of cerebellar ataxia: A two-phase, double-blind, auto-matched, pilot study. Clin Neurol Neurosurg. 2019 Jul; 182:123-129. doi: 10.1016/j.clineuro.2019.05.009. Epub 2019 May 14. PMID: 31121471.

BENUSSI, A. et al. Long-term clinical and neurophysiological effects of cerebellar transcranial direct current stimulation in patients with neurodegenerative ataxia. Brain Stimulation. 2017 Mar-Apr;10(2):242-250. doi: 10.1016/j.brs.2016.11.001. Epub 2016 Nov 3. PMID: 27838276.

BENUSSI, A. et al. A randomized, double-blind, sham-controlled, crossover trial. Neurology. 2018 Sep 18;91(12): e1090-e1101. doi: 10.1212/WNL.0000000000006210. Epub 2018 Aug 22. PMID: 30135258.

BENUSSI, A. et al. Therapeutic Potential of Non-Invasive and Invasive Cerebellar Stimulation Techniques in Hereditary Ataxias. Cells. 2023 Apr 20;12(8):1193. doi: 10.3390/cells12081193

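### The main goal names the effects of trans-spinal tDCS, but everyone gets tDCS and exercise together with no control group, so only change over the combined programme can be estimated.

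*Protocol*

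**What the plan says.** Section 2 (Aim) opens with "The main goal of this pragmatic clinical trial is to investigate the effects of trans-spinal tDCS in individuals with SCA", followed by gait and postural control under real-world conditions. The Abstract carries the same sentence. Neither mentions exercise.

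Section 3 (Design and Methods) describes the treatment: "Up to 45 patients with SCA of different types will undergo a non-invasive stimulation plus gait and postural control training". In each session participants will "simultaneously receive 20 min of trans-spinal tDCS and perform a gait training protocol with progressively greater difficulties, previously tested in patients with SCA". There are 20 sessions over four weeks. On comparison it states: "All participants will receive real stimulation, so there will be no control group". The reasons given are recruitment, transport and the ethics of withholding a possibly helpful treatment. No sham, exercise-only, crossover or run-in period is described.

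The same section sets the testing schedule:
- Timed up and go (TUG) and the modified dynamic gait index (mDGI) are done at baseline, after every five sessions and at one month.
- The Berg scale and the four-stage test are done at baseline, after session 20 and at one month.
- A one-leg stand test is done before and after each session.

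Specific aim (ii) and the Abstract's main question (i) do name tDCS given together with exercise. Aim (i) concerns patient characteristics that "can be identified to predict their improvement in balance and gait following tDCS sessions". Main question (ii) of the Abstract asks for characteristics "that can predict their improvement in postural control and gait following the 20 tDCS sessions".

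**The concern.** The sentence labelled as the main goal is the one from which the headline conclusion will be drawn. It names tDCS, and the design never lets tDCS vary apart from the exercise. Any observed change mixes stimulation with exercise, repeated testing, regression to the mean and disease course.

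Exercise is a serious rival explanation on the protocol's own account. The training targets gait and postural control, which are also primary outcome domains, and the reference list includes a dissertation on an exercise programme to improve balance in this disease. Section 1 (Scientific background) also treats concomitant challenge as important: "Therefore, the lack of challenges concomitant with the use of tDCS limits its results".

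The other components do not all pull the same way. Progression would push scores towards worsening, repeated testing probably towards improvement, and regression to the mean either way. A conclusion that tDCS improved gait and balance could be wrong by an amount, and in a direction, that these data cannot reveal.

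**Working it through.** The protocol states no effect size, standard deviation, alpha or power, and 45 is a ceiling without a derivation, so there is no figure to reproduce. The question is whether a tDCS effect is identifiable.

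**Inputs** (section 3): one tDCS and one exercise exposure per session; five sessions a week for four weeks; TUG and mDGI at baseline, after sessions 5, 10, 15 and 20, and one month later; up to 45 participants in one group.

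**Step 1: assessments 1 to 5.** Count what each participant has accumulated at each TUG or mDGI test.

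| Assessment | Intercept | tDCS sessions | Exercise sessions | Earlier tests | Weeks |
|---|---|---|---|---|---|
| 1 | 1 | 0 | 0 | 0 | 0 |
| 2 | 1 | 5 | 5 | 1 | 1 |
| 3 | 1 | 10 | 10 | 2 | 2 |
| 4 | 1 | 15 | 15 | 3 | 3 |
| 5 | 1 | 20 | 20 | 4 | 4 |

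The tDCS column equals the exercise column and is five times each of the last two. The rank is 2 of 5.

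**Step 2: what is estimable.** A contrast is estimable only if it lies in the row space of this matrix.
- Total change from assessment 1 to 5 is (0, 20, 20, 4, 4). This is row 5 minus row 1, so it is estimable.
- The tDCS contrast is c = (0, 1, 0, 0, 0). Take v = (0, 1, −1, 0, 0). Every row times v is 0, because tDCS and exercise counts are equal, but c·v = 1. The contrast is not in the row space and is not estimable.

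**Step 3: ways the data might rescue it.**
- *Follow-up.* Assessment 6 adds the row (1, 20, 20, 5, w), with w = 8, 8.3 or 8.5 weeks. The rank becomes 3 of 5, because time now separates from session count. The product with v is still 0, so tDCS is still not estimable.
- *More patients.* Stacking 45 participants repeats the same rows. The ranks stay at 2 without and 3 with follow-up.
- *Missed sessions.* With 3 to 5 sessions delivered per block at random, the rank is 3 for assessments 1 to 5. A missed session removes stimulation and exercise together, so the two columns stay equal and tDCS is still not estimable.

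**Step 4: amount of repeated testing by the end of treatment.** TUG and mDGI are at their fifth administration, and Berg and the four-stage test at their second. The one-leg stand has been tested on 20 × 2 = 40 occasions.

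**Step 5: illustration of the consequence.** Assume a true tDCS effect of zero, a two-sided alpha of 0.05, and a change from all other causes of d standard deviations of the change score. A paired t-test then has noncentrality d√n. The probability of a significant before-after change is:

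| d (assumed) | n = 45 | n = 200 |
|---|---|---|
| 0 | 0.05 | 0.05 |
| 0.1 | 0.10 | 0.29 |
| 0.2 | 0.26 | 0.80 |
| 0.3 | 0.50 | 0.99 |
| 0.5 | 0.91 | 1.00 |

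If any non-tDCS change is present, a larger trial makes a false attribution to tDCS more likely. With all 45 completing, the 95% interval for mean change has a half-width of t(0.975; 44)/√45 = 0.30 standard deviations of change. That precision applies to the combined programme, not to stimulation.

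**The case against.** The strongest reply is that the protocol never promises an isolated tDCS effect. The goal sentence does not say that exercise is excluded, and it continues with a real-world framing that suits a treatment package. The sentence after it in the Abstract, and aim (ii), both name exercise. Section 3 uses tDCS sessions as a label for the combined sessions, so the goal could be read as shorthand. The missing control group is admitted and justified, and the language about benefit is hedged. On this view the matter is one of wording only.

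Parts of this stand. The disclosure is real, and the choice of a single-group design is not challenged here. The shorthand reading is fair for aim (i) and main question (ii), where improvement following tDCS sessions is mainly a statement about time; these need clarification only. Some supporting points are also weaker than the main one:
- The background sentence can be read as exercise enhancing tDCS, not as exercise acting by itself.
- Eligibility sets no cut-off on the outcome scales, so regression to the mean is possible but not shown.
- The one-leg stand is not among the listed outcomes.
- The week counts assume that baseline falls just before session 1, and the count model treats exercise as a constant dose.

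None of this touches the central result, which needs only that the tDCS and exercise counts are equal in everyone. The reasons given for having no control group explain its absence, but nowhere does the protocol say what follows for the conclusions. A correct specific aim does not correct the sentence labelled the main goal. If the target is a pragmatic package, the goal should name the package.

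**Conclusion.** The concern holds. The main goal as worded cannot be answered by this design. Before-after change during the combined programme can be estimated, and so can baseline factors associated with that change. The contribution of tDCS cannot be estimated at any n, and no analysis plan can repair that. The result rests on each session delivering one exposure to each component and on missed sessions losing both; one month was taken as 4 to 4.5 weeks. No bias can be quantified, and the probabilities in the illustration depend on assumed values of d. The wording should be corrected, because it determines what the trial may conclude.

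**What to change.** 1. In the Abstract and section 2, restate the main goal as: *change in gait and postural control over a combined 20-session programme of trans-spinal tDCS plus progressive exercise*.
2. Clarify aim (i) in section 2 and main question (ii) in the Abstract as: *baseline factors associated with change over the combined programme, not predictors of response to tDCS*.
3. Add one sentence: *without a comparator, observed change and its predictors will not be attributed to stimulation; change during the programme also includes exercise, repeated testing, regression to the mean and disease course*.

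The added sentence also governs how aims (ii) and (iv) and main question (i) are read, so their wording can stay. Section 1 needs no change.

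The cost is a few sentences, with no extra patients, visits or tests. The claim becomes more modest: whether stimulation itself works is left unanswered by this trial.

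### The anode is meant for the cerebellar region, but the only placement step measures 2 cm above the inion; a pad centred there lies 79-90% above that landmark.

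*Protocol*

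**What the plan says.** All the relevant text on placement is in the protocol, section 3 (Design and Methods). The overview of the intervention describes stimulation "with the anodic electrode positioned over the cerebellar region and the cathodic electrode over the thoracic region of the spinal cord". The equipment paragraph repeats the target and introduces the method: "The anode electrode will be positioned over the cerebellar region. To do this, the inion region will be located". A tape measure is then used, and "the point 2cm above the inion will be identified and the electrode will be fixed to the scalp".

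The electrodes are "a pair of 5x7 cm (35 cm²) electrodes wrapped in sponges moistened with saline solution". The protocol does not say whether the 5 cm or the 7 cm side is vertical, or whether the centre or an edge of the pad goes on the mark. No other part of the protocol gives a different anode landmark.

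Section 1 (Scientific background) bases the rationale on earlier trials of "transcranial direct current stimulation (tDCS) over the cerebellum and spinal cord (trans-spinal stimulation"). Section 3 also states: "All participants will receive real stimulation, so there will be no control group".

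**The concern.** The target and the step for reaching it do not agree. The step is presented as the means of placing the anode over the cerebellar region, yet it measures upward from the inion. The cerebellum lies below about the level of the inion, and the scalp above it covers the occipital lobes. An operator who follows the instruction therefore moves the pad off the named target. The simplest explanation is that the direction was written the wrong way round, but the protocol alone cannot confirm this.

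Electrode site is part of what defines a stimulation intervention. All participants receive the same active stimulation, so an error here applies to the whole trial. If the step is followed with a centred pad, calling the anode cerebellar would not describe where it was placed. Anyone repeating the procedure would have to choose between the stated target and the stated measurement.

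The stakes should not be overstated. There is no control group and training is given during stimulation, so a before-after change could not be credited to any particular electrode site even with perfect placement. No endpoint, sample size or error rate is affected.

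**Working it through.** **Inputs from the protocol, section 3:** anode offset 2 cm above the inion; pad 5 x 7 cm; up to 45 participants; 20 sessions each.

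**The plan's own figure.** Pad area = 5 x 7 = 35 cm², as stated.

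**Assumptions, not in the protocol:**
- The upper limit of the cerebellum is at about the level of the inion (varied below).
- The pad is centred on the mark (varied below).
- The pad is treated as a flat rectangle.

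**Formula.** Heights are in cm relative to the inion, with + meaning above. For a pad with vertical side h centred at c, the share of its area above a level L is (c + h/2 - L)/h, bounded between 0 and 1.

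**Step as written, pad centred (c = +2, L = 0):**
- 5 cm side vertical: the pad runs from -0.5 to +4.5; share above = 4.5/5 = 90%.
- 7 cm side vertical: the pad runs from -1.5 to +5.5; share above = 5.5/7 = 79%.

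**If the pad is not centred (L = 0):**

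| Part of pad on the +2 cm mark | 5 cm vertical | 7 cm vertical |
|---|---|---|
| Centre | 90% | 79% |
| Upper edge | 2/5 = 40% | 2/7 = 29% |
| Lower edge | 100% | 100% |

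The full range over these readings is 29-100%.

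**If the upper limit of the cerebellum is not exactly at the inion (pad centred at +2):**

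| Assumed limit L | 5 cm vertical | 7 cm vertical |
|---|---|---|
| +2 | 2.5/5 = 50% | 3.5/7 = 50% |
| +1 | 3.5/5 = 70% | 4.5/7 = 64% |
| -1 | 5/5 = 100% | 6.5/7 = 93% |

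For a limit within 1 cm of the inion either way, 64-100% of a centred pad lies above it. The share falls to half only if the limit is 2 cm above the inion.

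**Both assumptions relaxed in the plan's favour.** With the upper edge at +2 and the limit at +1, the share above the limit is 1/5 = 20% or 1/7 = 14%.

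**Direction reversed, pad centred at -2 (L = 0):** 0.5/5 = 10% (5 cm vertical) or 1.5/7 = 21% (7 cm vertical) lies above the inion.

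**Sessions governed by the instruction:** 45 x 20 = 900 at most.

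**What cannot be computed.** Pad area on the scalp is not the volume of tissue stimulated, and the cathode lies far below, near T11. The protocol gives nothing from which to derive the current reaching the cerebellum.

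**The case against.** The strongest reply is that the contradiction is not in the text alone. The protocol never says where the cerebellum lies relative to the inion, so outside anatomy is needed to see a conflict. That is true, but it is elementary surface anatomy, not a recalled study result, and moving the limit by 1 cm either way does not change the conclusion for a centred pad.

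The second reply is that centring is inferred. The cathode instruction in the same paragraph explicitly fixes the pad at the measured point; the anode sentence only has the point identified and the electrode fixed to the scalp. With the upper edge on the mark, 60-71% of the pad would lie below the inion and little conflict would remain. This stands as a reason to give 79-90% only with its condition and to show the wider range. It does not rescue the instruction: nothing in the text suggests an edge placement, a point is normally measured so that the electrode can be put on it, and an edge placement would itself have to be stated.

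Third, current may still reach the cerebellum from a pad placed higher, and no loss of effect has been shown. This stands in full, which is why no bias is claimed.

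Fourth, 2 cm above may be deliberate, and 2 cm below appears nowhere in the protocol as an anode position. That is possible. In that case the description of the site is what needs to change.

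**Conclusion.** The concern holds. The protocol states the anode target twice and gives one step to reach it, and that step leads away from the target. With the pad centred on the mark and the cerebellum lying below about the level of the inion, 79-90% of the pad is above the landmark; allowing 1 cm either way for anatomy, 64-100% is above the cerebellar limit. Without the centring assumption, the share above the inion is 29-100%.

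The mismatch should be corrected. Confidence is medium, because the conclusion rests on two assumptions that the protocol does not state. What is damaged is correct delivery of the intervention and an accurate account of it, in up to 900 sessions. The physiological consequence is unknown. The level of the cathode is a separate matter.

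**What to change.** The sponsor should confirm the intended position and rewrite the one sentence in section 3.

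- **If the cerebellum is the target:** locate the inion, mark the point 2 cm below it, centre the pad on that point, and state whether the 5 cm or the 7 cm side is vertical.
- **If 2 cm above the inion is intended, or has already been used:** keep the measurement, state the centring and orientation, and describe the anode by that position, not as cerebellar, throughout the protocol and in reports.

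The cost is one corrected sentence, plus a consistent site description under the second option. No extra visits, staff, equipment or participants are needed.

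### The protocol gives T8 as the cathode level, but its overview and placement steps both lead to about T11, and those steps cannot reach T8

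*Protocol*

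**What the plan says.** All the text on cathode position is in the protocol, section 3 (Design and Methods). It gives the position three times.

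- **Overview of the intervention:** "the cathodic electrode over the thoracic region of the spinal cord (approximately vertebra T11").
- **Detailed description, level:** "The cathode electrode will be positioned over the spinal region, more precisely, at the level of T8".
- **Detailed description, procedure:** "To precisely find this position, the thoracic spinous processes will be palpated, and the 11th process located". Staff then measure with a tape: "identify the point located 2 cm below T11 and fix the electrode with adhesive tape at this point".

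The electrodes are "a pair of 5x7 cm (35 cm²) electrodes wrapped in sponges moistened with saline solution". The protocol does not say whether the centre or an edge of the pad goes on the marked point, or which side of the pad runs along the spine. No other section gives a cathode level.

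**The concern.** The procedure is introduced as the way to find the level just named, and that level is T8. It uses a landmark three vertebrae lower and an offset in the wrong direction. The level and the method for reaching it cannot both be right.

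This matters because the cathode is the only electrode on the spine in a trial of trans-spinal stimulation, and the passage is the operative description of a treatment given in 20 sessions to up to 45 patients. There are three possibilities:

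- **T11 intended, steps followed.** Placement is uniform at about T11. The harm is a wrong level in the protocol and in any report or replication that copies it.
- **T8 intended, steps followed.** Participants receive a different montage from the one planned.
- **Some operators act on the T8 sentence.** Placement differs between participants. The text makes this possible but does not show that it happens.

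**Working it through.** The protocol gives no figure to reproduce. The check compares its statements and then sizes the gap.

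**Direction (no assumption needed).** Thoracic levels are numbered downward, so T8 is 11 − 8 = 3 levels above T11. The procedure starts at T11 and goes 2 cm below it. It therefore ends further from T8 than it began.

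**Inputs for the size.** From the protocol: landmark T11, offset 2 cm downward, pad 5 x 7 cm. Assumed, because the protocol does not give it: spacing *s* = 2.0 to 2.5 cm per thoracic level, with 3 cm as a wider upper limit. Pads are taken as centred on their points.

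**Do the overview and the steps agree?** Two pads centred 2 cm apart share:
- 5 cm side along the spine: (5 − 2)/5 = 60%
- 7 cm side along the spine: (7 − 2)/7 = 71%

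They do, within the size of the pad.

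**How far is T8 from the taped point?** Distance = 3*s* + 2.
- *s* = 2.0: 6.0 + 2 = 8.0 cm
- *s* = 2.5: 7.5 + 2 = 9.5 cm
- *s* = 3.0: 9.0 + 2 = 11.0 cm

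**Would pads at the two sites overlap?** With the 7 cm side along the spine, which is the arrangement most favourable to overlap, the edge-to-edge gap is 3*s* + 2 − 7:
- *s* = 2.0: 1.0 cm
- *s* = 2.5: 2.5 cm

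There is no overlap whenever 3*s* + 2 ≥ 7, that is, *s* ≥ 5/3 = 1.67 cm per level.

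**Could it be a slip of below for above?** Two cm above T11 would lie 3*s* − 2 from T8:
- *s* = 2.0: 4.0 cm
- *s* = 2.5: 5.5 cm

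That still falls well short of T8.

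**Could placing the pad by its lower edge rescue T8?** With the lower edge on the taped point, the upper edge is 5 − 2 = 3 cm or 7 − 2 = 5 cm above T11. T8 is 6 to 9 cm above T11 for *s* = 2 to 3. The pad stops 6 − 5 = 1 cm to 9 − 3 = 6 cm short.

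**The case against.** The strongest reply is that this is one wrong label. An operator has a complete sequence to follow (palpate, find the 11th process, measure 2 cm down, tape), and the overview agrees with it. T8 appears once. If T8 is simply a drafting error, the delivered treatment is unchanged, and no endpoint, sample size or analysis depends on it. For T8 to be right, the overview, the palpated process and the taped point would all have to be wrong, which is the least economical reading. This stands as far as it goes: T8 is probably the error, and the worse outcomes are conditional.

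The distances can also be questioned. Spacing per level is assumed, and the no-overlap result depends on how the pads are anchored. If the pad at the taped point is fixed by its lower edge with the 7 cm side vertical, it reaches 5 cm above T11. A pad centred on T8 would have its lower edge 6.0 − 3.5 = 2.5 to 7.5 − 3.5 = 4.0 cm above T11, so the two would overlap by 1.0 to 2.5 cm. That is correct, but it anchors one pad by its edge and the other by its centre, and the pad at the taped point still does not reach T8. The contradiction itself does not rest on these distances.

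Finally, session records and a retrospective check go beyond correcting a sentence, and the protocol does not show that anyone has been treated or that the site goes unrecorded. Hence the check below applies only to participants already treated, if there are any.

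None of this makes the text consistent. The sentence that presents itself as the more exact one names a level that its own instructions do not deliver.

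**Conclusion.** The concern holds: the text is wrong as written and should be fixed. That the steps cannot reach T8 follows from the protocol alone. The size of the miss, 8.0 to 9.5 cm with no overlap between centred pads, rests on an assumed 2.0 to 2.5 cm per level; at 3 cm per level it would be 11 cm. About T11 is the more likely intention, since the overview and the steps both support it, but only the sponsor can confirm that. The consequence is for what was delivered and whether it can be reproduced. There is no effect on type I error, power or between-group comparison.

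**What to change.** State one target level in section 3 and make the overview, the level sentence and the landmark steps agree.

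- **If about T11 is intended:** replace T8 in the level sentence with the 11th-process landmark.
- **If T8 is intended:** change the palpated process and the overview. Changing below to above is not enough.

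State also whether the pad is centred on the marked point and which side runs along the spine, so that the written position is complete. From then on, record the site used at each session. For any participants already treated, check with the treating staff and any existing notes which site was used, and report the result.

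The cost is one protocol correction and a brief entry per session. The retrospective check takes staff time and may be incomplete if the site was not noted.
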